### **Evaluation of the Practice Facilitation Intervention: Implementation and Clinical Outcomes.**

Aim 3 implementation and clinical-specific outcomes were derived guided by the RE-AIM (Reach, Effectiveness, Adoption, Implementation, and Maintenance) evaluative framework, often used to guide implementation evaluations. RE-AIM will be assessed using EHR data pulled from VA's Corporate Data Warehouse (CDW). The data pull will include data from January 1, 2019 – December 31, 2023, to evaluate these outcomes, which includes the pre-intervention period, the active facilitation intervention period, and the post-facilitation intervention period (i.e., 3-, 6-, and 12-months after active implementation). RE-AIM constructs are defined as follows:

**Reach** of alcohol-related care will be assessed at the patient level using EHR data, pulled from VA's CDW. **Reach** outcomes will be expressed as a rate, with the

denominator (for all outcomes) defined as all Veterans with a visit to the Pittsburgh VA primary care clinic during the practice facilitation intervention. The numerator for each Reach outcome is as follows: the number of Veterans who screened positive for unhealthy alcohol use (AUDIT-C  $\geq$  5) AND had any documented brief intervention, encounters with primary care-mental health integration (PC-MHI), encounters with PACT/ Whole Health clinical pharmacists, specialty addictions treatment (inpatient and outpatient clinic visits for substance use disorder treatment encounters with an accompanying AUD diagnosis), or pharmacotherapy for AUD (any filled prescription for FDA-approved medications: acamprosate, disulfiram, or oral/injectable naltrexone or non-FDA approved effective medications: gabapentin, baclofen, or topiramate) in the 30 days following a positive screen. Denominators will also be derived to represent specific subpopulations (e.g., women, Black and Hispanic Veterans). Rates at the start of the practice facilitation intervention and at 3- and 6-months post intervention will be calculated to examine change in Reach outcomes over time.

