**Adoption** is identified as the percentage of providers from the PC clinic who deliver alcohol-related care when a Veteran screens positive for unhealthy alcohol use. Specifically, we will use data available in the EHR to examine delivery of brief interventions, consults placed to PC-MHI/clinical pharmacists or specialty addictions treatment and providing pharmacotherapy for AUDs at the provider and clinic level. Rates of alcohol-related care pre-intervention (2019-2022), during the course of the practice facilitation intervention (July 2022-December 2022), after the intervention (e.g., 3- and 6-months post intervention (Jan 1, 2023-March 31, 2023, and Jan 1, 2023-June 30, 2023 respectively) will be used to measure whether adoption rates of alcohol-related care increased over time.

**Maintenance** is defined as the extent to which evidence-based alcohol care becomes routine and part of the PC culture (care sustained over time). Reach and Adoption outcomes using EHR data will be assessed at 12-months post intervention (Jan 1, 2023-Dec. 31, 2023) to examine whether high-quality alcohol care was sustained.

**Effectiveness** is defined as the prevalence of unhealthy alcohol use at 12-months post-intervention (Jan 1, 2023-Dec. 31, 2023) as measured by AUDIT-C scores pulled from the EHR. This variable will also be expressed as a rate with the denominator defined as all Veterans with a visit to PC during the practice facilitation intervention (same as for Reach outcomes). The numerator will be the number of Veterans with an encounter in PC who screened positive for unhealthy alcohol use (AUDIT-C  $\geq$  5) at 12-months post facilitation intervention. While it is unlikely that a pilot study will have a measurable

impact on clinical outcomes, measuring effectiveness will serve as pilot data for a larger trial.

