#### **5.7 Data Analysis**

**Implementation Outcomes:** Reach outcomes will be reported descriptively (e.g., percentage of patients with an AUDIT-C  $\geq 5$  who were offered a BI or pharmacotherapy for AUD) and compared pre- (2019-2022) and post-implementation (at 3- and 6-months) to see whether Reach of alcohol care increased over time. Adoption outcomes via EHR will be descriptive, and include percentages, frequencies, and means (SD) of alcohol-related care by provider and clinic to understand whether Adoption of high-quality alcohol-related care increased over time. Descriptives will be examined and compared at the start of Active Implementation and at 3- and 6-months post Active Implementation. Reach and Adoption rates will again be examined at 12-months post Active Implementation and compared to rates at 3- and 6-months to see if high-quality alcohol-related care was sustained (Maintenance). **Effectiveness outcomes:** Effectiveness will be assessed via a time-series analysis, where the intervention site will serve as its own control, and we will investigate whether Veterans' with an encounter in Pittsburgh VA Primary Care during the implementation intervention reduced their drinking 12-months post intervention using AUDIT-C scores in the EHR. Time-series analysis was chosen because historical trend is accounted for in the analytic model, results can be displayed graphically, and the size of the effect can be estimated at different times post

intervention. The outcome (AUDIT-C scores) will be modeled using a regression model with an indicator for practice facilitation (pre- vs. post-), a continuous term for time (days since practice facilitation dissemination) and the interaction between the two. The indicator variable will assess immediate changes in AUDIT-C scores post implementation intervention, while the interaction term will assess if there is a change in the slope of AUDIT-C scores pre- and intervention at 12-months. While there is controversy over whether pilot studies should assess clinical efficacy or effectiveness, we decided to examine it here as a training opportunity and as preparation for a possible hybrid effectiveness-implementation Merit trial investigating practice facilitation as a way to improve alcohol-related care on a larger scale.

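### Maintenance compares a 12-month rate with the 3- and 6-month rates nested inside it, so a late-2023 fall in care is diluted or, on one stated denominator, cannot show as a fall

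*Combined protocol and SAP*

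**What the plan says.** The windows are set out in section 5.1, under the evaluation of the practice facilitation intervention. The Adoption paragraph dates the early post periods as "3- and 6-months post intervention (Jan 1, 2023-March 31, 2023, and Jan 1, 2023-June 30, 2023 respectively", introduced as examples. The Reach paragraph names 3 and 6 months without dates. For Maintenance the protocol covers both outcomes: "Reach and Adoption outcomes using EHR data will be assessed at 12-months post intervention (Jan 1, 2023-Dec. 31, 2023".

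Section 5.7 states the comparison: "Reach and Adoption rates will again be examined at 12-months post Active Implementation and compared to rates at 3- and 6-months". Reach and Adoption are to be reported descriptively. The only time-series model in the plan is for AUDIT-C scores.

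Two Reach denominators appear. Section 5.1 uses every Veteran with a clinic visit during the facilitation period, for all Reach outcomes. The example in section 5.7 is a percentage among patients with AUDIT-C of 5 or more. Adoption is the percentage of clinic providers who deliver care after a positive screen. The protocol does not say whether one delivery is enough to count.

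Reach counts care "in the 30 days following a positive screen". On the data: "The data pull will include data from January 1, 2019 – December 31, 2023, to evaluate these outcomes".

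**The concern.** Maintenance asks whether care persisted once facilitation had ended, which is a question about the later part of 2023. The plan answers it with a rate pooled over the whole year and sets that rate against two of its own components. The early months, when any carry-over from facilitation should be strongest, sit on both sides of the comparison and pull the 12-month figure towards the 3- and 6-month figures.

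The risk is that care is reported as sustained when it was not. Reach and Adoption are the main implementation outcomes of this pilot, and section 5.7 presents the work as preparation for a possible larger trial, so a wrong reading could carry into that design.

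A second, smaller matter is that the 12-month window and the data pull end on the same day. Reach needs 30 days after each screen, so the last screens are followed for too short a time.

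**Working it through.** The plan gives no rate, sample size or power for Maintenance, so there is no figure to reproduce. What follows is date arithmetic with labelled assumptions.

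**Window lengths (dates from section 5.1).** January 1 to March 31 is 90 days, to June 30 is 181 days, and to December 31 is 365 days. The 3-month window is 90/365 = 24.7% of the 12-month window, and the 6-month window is 181/365 = 49.6%.

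**Reach as a percentage of positive screens (section 5.7).** If the rate drops at some date, the part of the drop visible in the 12-month rate equals the share of the year's positive screens that fall after that date. With screens spread evenly (assumed):

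- loss from July 1: 184/365 = 50.4% visible
- loss from October 1: 92/365 = 25.2% visible

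These fractions do not depend on the rates. They do depend on even spacing: if 40% to 60% of positive screens fell after July 1, the visible part would be 40% to 60%. As an illustration, assume 60% of positives receive care, falling to 40%:

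| Scenario | 3-month | 6-month | 12-month as planned | October-December alone |
|---|---|---|---|---|
| No loss | 60% | 60% | 60% | 60% |
| Loss from July 1 | 60% | 60% | (60×181 + 40×184)/365 = 49.9% | 40% |
| Loss from October 1 | 60% | 60% | (60×273 + 40×92)/365 = 55.0% | 40% |

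**Reach on the fixed cohort (section 5.1).** The denominator is constant and the numerator only accumulates, so the rate can stay level or rise but not fall. Take the roughly 10,000 Veterans of section 5.2, and assume that 10% (1,000) screen positive evenly over 2023 and that 60% of them receive care. The rate at day T before any loss is (1,000/365 × 0.60 × T)/10,000.

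| Scenario | 3-month | 6-month | 12-month |
|---|---|---|---|
| No loss | 1.5% | 3.0% | 6.0% |
| 60% to 40% from July 1 | 1.5% | 3.0% | 5.0% |
| All care stops July 1 | 1.5% | 3.0% | 3.0% |

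The second row rises although care has dropped by a third. The third row looks stable although care has ceased. A different positive rate rescales every entry and leaves the pattern unchanged.

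**Adoption.** If one delivery makes a provider an adopter and the provider list is fixed, Adoption behaves in the same way. Suppose each provider has a 10% chance per month of delivering care (assumed). Constant behaviour then gives 1 − 0.9³ = 27%, 1 − 0.9⁶ = 47% and 1 − 0.9¹² = 72% at 3, 6 and 12 months. If delivery ended on June 30, the 12-month figure would stay at 47%.

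**Follow-up at year end (Reach only).** A December 1 screen completes 30 days on December 31. Screens on December 2-31 do not, which is 30/365 = 8.2% of the year. If care is spread evenly over the 30 days, the loss is (1 + 2 + … + 30)/30 = 15.5 screen-days of care. At a constant care rate the relative undercount is:

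| Care given on the day of the screen (assumed) | Full year (÷365) | July-December (÷184) | October-December (÷92) |
|---|---|---|---|
| 0% | 4.2% | 8.4% | 16.8% |
| 50% | 2.1% | 4.2% | 8.4% |
| 80% | 0.8% | 1.7% | 3.4% |
| 100% | 0 | 0 | 0 |

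This error lowers the last rate, while nesting props it up. Nothing suggests that the two would cancel.

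**The case against.** The strongest reply is that a decline would still be seen. On the section 5.7 denominator it would: 60% to 49.9% is a visible fall. The records are dated, so an analyst could subtract the 6-month counts from the 12-month counts to recover July-December. This stands in part. It means the defect is correctable after extraction. But the plan does not call for the subtraction, and subtraction does not rescue an ever-delivered Adoption measure, where it yields only providers who deliver for the first time.

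The 3- and 6-month dates appear only under Adoption and as examples, so their use for Reach is inferred. That is a fair limit. They are the only dates given, however, and the 12-month window starting January 1 is stated for both outcomes.

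A reader might infer that overlapping samples give the comparison the wrong variance. The documents do not support this as a fault: these outcomes are descriptive and no test or interval is planned for Maintenance. A reader might also take the year-end undercount to affect every final rate. It does not, because the 30-day period is stated for Reach and not for Adoption, and over the planned full-year window the effect is small.

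Finally, splitting off July-December as a third window after January-March and April-June would not be enough. Windows of 90, 91 and 184 days would still raise the last rate mechanically on a fixed denominator or an ever-delivered measure. This objection stands and shapes the fix.

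**Conclusion.** The nesting is a real defect in the Maintenance comparison and follows directly from the stated dates. Nothing elsewhere in the protocol gives Reach or Adoption a separate late-2023 window or a monthly series.

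Its size depends on which denominator is used. On the percentage-of-positives reading, a loss is diluted to about 50% of its size (from July 1) or 25% (from October 1), assuming evenly spread screens. It would be too strong to say that it is hidden. On the fixed cohort denominator, or for ever-delivered Adoption with a fixed provider list, the cumulative figure cannot fall, and even a total stop looks like stability.

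The missing follow-up is secondary and confined to Reach: about 0-4.2% relative over the year under the care timings tried. It matters more once late 2023 is examined separately, so the two corrections belong together. The care rates, positive-screen rate, monthly delivery chance and same-day shares used above are all assumptions; the documents give none of them.

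**What to change.** 1. Replace the nested windows with disjoint ones of equal length, for example the calendar quarters of 2023 (90, 91, 92 and 92 days) or January-June against July-December (181 and 184 days). Quarters show an October loss in full; half-years show 92/184 = 50% of it but hold more screens. State the dates for both Reach and Adoption.
2. In each window, take as denominator the Veterans who screened positive in that window (Reach) and the providers with at least one positive screen in that window (Adoption). Reconcile the Reach denominators of sections 5.1 and 5.7 accordingly.
3. Define Maintenance as the late-2023 rate, compared descriptively with the early post-intervention, active and pre-intervention rates. For Adoption, cut the earlier periods into blocks of the same length.
4. For Reach, stop index screens at December 1, 2023, or extend the pull to January 30, 2024. With the December 1 stop, the last quarter has 62 days of screens (92 − 30) and the second half-year 154 (184 − 30). The within-window denominator keeps this from lowering the rate mechanically.

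Cost: items 1 to 3 are changes of wording and a re-tabulation of dated records already in the pull. The December 1 stop needs no new data. Extending the pull goes beyond the dates in sections 5.1 and 5.2, in a document that also requests consent and HIPAA waivers (section 5.3), so it may need an amendment. The main downside is fewer positive screens per window and hence less precise rates.

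### Effectiveness is defined as the 12-month rate of AUDIT-C ≥5, but the only planned pre/post analysis is of AUDIT-C scores, and no pre-facilitation value of the rate is specified

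*Combined protocol and SAP*

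**What the plan says.** Section 5.1, under the evaluation of the practice facilitation intervention, says that Effectiveness "is defined as the prevalence of unhealthy alcohol use at 12-months post-intervention", and names one window for it, January to December 2023. On its form: "This variable will also be expressed as a rate with the denominator defined as all Veterans with a visit to PC during the practice facilitation". On the count: "The numerator will be the number of Veterans with an encounter in PC who screened positive for unhealthy alcohol use", meaning AUDIT-C ≥5 at 12 months after facilitation. No earlier time point is given for this rate.

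Section 5.7 gives the only Effectiveness analysis: "Effectiveness will be assessed via a time-series analysis, where the intervention site will serve as its own control". The dependent variable is then named: "The outcome (AUDIT-C scores) will be modeled using a regression model with an indicator for practice facilitation (pre- vs. post"), with a continuous time term and their interaction. The effect terms are in the same units: "The indicator variable will assess immediate changes in AUDIT-C scores post implementation intervention", and the interaction is for a change in the slope of the scores. No link function or distribution is stated. Neither the threshold of 5 nor the rate appears in the Effectiveness part of 5.7.

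The raw material for an earlier rate will be in hand. Section 5.1 says: "The data pull will include data from January 1, 2019 – December 31, 2023, to evaluate these outcomes, which includes the pre-intervention period".

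**The concern.** The variable that defines Effectiveness and the variable that is analysed for it are not the same. Followed as written, the study will produce two Effectiveness results: a prevalence for 2023 with nothing specified to set beside it, and level and slope changes in AUDIT-C scores. The first cannot show change. The second can show change, but not whether unhealthy use as defined became less common. The plan does not say which of the two is the Effectiveness result if they point different ways.

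The omission does not look like shorthand, because the plan writes out comparisons for its other rates. For Reach, section 5.1 says "Rates at the start of the practice facilitation intervention and at 3- and 6-months post intervention will be calculated", and 5.7 adds a comparison of 2019–2022 with the post-implementation period. Adoption has pre, during and post windows. Section 5.7 also uses the ≥5 threshold explicitly for Reach, then moves to scores for Effectiveness.

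At stake is the reading of the pilot. Section 5.1 intends the Effectiveness result to serve as pilot data for a larger trial, and a score change could be taken as a change in unhealthy use, or its absence as no change.

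**Working it through.** The documents give no baseline prevalence, SD, effect size, alpha or power, so there is no stated figure to reproduce. The check has three parts.

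**1. Text side by side**

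| Item | Section 5.1 | Section 5.7 (Effectiveness) |
|---|---|---|
| Variable | AUDIT-C ≥5, yes/no, as a rate | AUDIT-C scores |
| Time | January–December 2023 only | Pre versus post, with time trend |
| Denominator | All Veterans with a primary care visit during facilitation (July–December 2022) | Not restated as a rate; only recorded scores can enter |
| Comparison | None stated | Level change and slope change |

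**2. Can a score result stand in for the rate?** Both distributions below are assumed and serve only to test this. The mean is Σ(score × share); the prevalence is the sum of shares at scores 5 and above.

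*Distribution I.* Shares: 0: 40%, 1: 15%, 2: 12%, 3: 10%, 4: 8%, 5: 5%, 6: 4%, 7: 3%, 8: 2%, 10: 1%. Mean = 0.15 + 0.24 + 0.30 + 0.32 + 0.25 + 0.24 + 0.21 + 0.16 + 0.10 = 1.97. Prevalence = 5 + 4 + 3 + 2 + 1 = 15%.

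| Change | Mean | Prevalence |
|---|---|---|
| Half of those at 1–4 drop one point: 0.5 × 45% = 22.5% | 1.97 − 0.225 = 1.745 | 15% |
| Scores of 8 fall to 6 and of 10 to 7 | 1.97 − 0.04 − 0.03 = 1.90 | 15% |
| All 5s fall to 4; 5% of Veterans move from 0 to 1 | 1.97 − 0.05 + 0.05 = 1.97 | 10% |
| All 5s fall to 4; 10% of Veterans move from 0 to 1 | 1.97 − 0.05 + 0.10 = 2.02 | 10% |

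In the last row the mean rises while prevalence falls, so even the direction can differ.

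*Distribution II.* Shares for scores 0–12: 40, 16, 12, 11, 10, 4, 2.5, 1.5, 1.2, 0.7, 0.5, 0.3, 0.3%. Mean 1.863, SD 2.24, prevalence 11.0%.

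- A quarter of those at 5–6 move to 4. Prevalence falls by 0.25 × 6.5 = 1.6 points, to 9.4% (15% relative). The mean moves by −(0.01 × 1 + 0.00625 × 2) = −0.0225, about 1% of an SD.
- One in ten of those at 1–4 drops a point. The mean moves by −0.10 × 0.49 = −0.049; prevalence stays at 11.0%.
- Forty per cent of all those at ≥5 drop a point. Prevalence falls by 0.40 × 4% = 1.6 points, again to 9.4%, but the mean moves by −0.40 × 0.11 = −0.044.

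The first and third changes give the same fall in prevalence with a twofold difference in the mean shift. The size of any divergence depends on who moves and how far.

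**3. The denominator.** A Veteran without a 2023 screen stays in the section 5.1 denominator but cannot enter the numerator. The rate is then (prevalence among the screened) × (share screened). Taking 15% among the screened as an assumption:

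| Share screened (assumed) | Rate |
|---|---|
| 100% | 15.0% |
| 90% | 13.5% |
| 80% | 12.0% |
| 70% | 10.5% |

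A pre-period rate is comparable only if the rule is the same and the share screened is reported in both periods.

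**The case against.** A reader might infer that Effectiveness is never compared with anything. The documents do not support that. Data from 2019 onward are extracted, the site is its own control, and 5.7 plans a pre/post comparison for Effectiveness. What is missing is narrower: a specified earlier value and comparison for the rate. Such a value could be derived; none is written in.

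A reader might also take it as settled that 5.7 models the mean score. The text says only a regression model for scores. A model of the average is the natural reading of level and slope changes in scores, but it is an inference. If a binary model was meant, the text needs correcting all the same.

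The best defence of the plan is that 5.1 says prevalence is measured through AUDIT-C scores and adds that the variable will also be a rate, so the score could be the measure and the rate an extra description. The word also may equally mean in the same way as Reach, and the sentences that follow fix a rate with a ≥5 numerator. This softens the conflict without removing it. It does make redefining Effectiveness as the score a legitimate repair.

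Two further points stand. The illustrations rest on assumed distributions and chosen scenarios: they show that divergence is possible, not that it is likely or large. And the plan is modest about this analysis. It expects no measurable clinical effect from a pilot, describes the analysis as training and preparation, and ties no go/no-go or sample-size rule to it.

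**Conclusion.** The point holds in this form: the defined Effectiveness rate has no specified pre-facilitation value or comparison, and the planned pre/post analysis applies to a different variable whose result does not determine the rate. This conclusion rests on the text alone. Its practical size cannot be derived from the documents; under the assumed distributions the outcomes can differ in size (prevalence down 15% relative with a mean shift of about 1% of an SD) and in direction (mean 1.97 to 2.02 while prevalence falls from 15% to 10%). The consequence is limited by the pilot's stated purpose, but the mismatch should be corrected before the analysis is run.

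**What to change.** - **Section 5.7.** Fit the same segmented time-series to AUDIT-C ≥5 (yes/no; logistic or linear-probability) alongside the score model. Report the fitted 12-month prevalence with facilitation and as projected without it. State the link or distribution of the score model.
- **Section 5.1.** Add the same rate for the 12 months before facilitation, July 2021–June 2022, with one numerator and denominator rule in both periods.
- **Denominator.** State it explicitly. Section 5.1 uses all Veterans with a visit during facilitation, whereas a model of AUDIT-C ≥5 can use only those with a recorded screen. Report the rate among screened Veterans with the number screened in each period, and say whether the pre-period rate uses the same Veterans or those seen in the earlier window.
- **Status.** Declare in advance which variable is the Effectiveness outcome. If the sponsor prefers the score, redefine Effectiveness in 5.1 as the AUDIT-C score and report the pre and post prevalence as secondary.

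The cost is one extra model and one extra rate from data already in the extraction. The binary outcome is less precise than the score, which is a reason to keep both.

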## **5.2 Recruitment Methods**

Ann Arbor regulatory approval is being requested only for the data analysis portion of AIM 3 (extraction, cleaning, and analysis of AIM 3 outcome data from the VA's electronic health record via the Corporate Data Warehouse). All recruitment, enrollment and intervention activities were completed at the Pittsburgh VA.

Approximately 10,000 Veterans' data will be pulled from the CDW to examine implementation and clinical outcomes. Data to evaluate implementation and clinical effectiveness outcomes will be obtained electronically and securely from already collected administrative databases, using scrambled SSN or Patient ICN to link data together. Data sources will include the CDW, Health Factors (AUDIT-C and Brief Intervention information), Vital Status File to obtain DOB for calculating age of Veterans, and Prescription/Pharmacy information (for data on whether medications for alcohol use disorder were prescribed). Other specific records include: sociodemographics (e.g., sex, gender identity, marital status, indicator of socioeconomic status, race/ethnicity, sexual orientation), past-year diagnoses (Alcohol use disorder diagnosis, Substance use disorder diagnoses, Tobacco use disorder diagnosis, Mental Health disorder diagnosis (Depression, anxiety, PTSD, Bipolar, Psychotic-spectrum)), index of medical complexity (e.g., Charlson index, VA CAN score) utilization of primary care services pre-implementation (2019-2022), during (July 2022 - Dec. 2022) and post-implementation intervention (Jan 2023 - Dec. 2023), referral and utilization of substance use services in the past year (yes/no), and referral and utilization of past-year mental health services (yes/no). Data may also be reviewed within CAPRI/Joint Legacy Viewer (JLV) to allow study team members to look into potential data anomalies from our dataset. In addition, members of the study team may review notes, charts, dates of AUDIT-C administration, etc. to verify the accuracy of our Aim 3 dataset.

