#### **5.4 Inclusion/Exclusion Criteria**

We will include all Veterans with a visit to the Pittsburgh VA primary care during the practice facilitation intervention.

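### The 12-month Effectiveness rate keeps Veterans with no 2023 AUDIT-C in its denominator, so they count as not screening positive and prevalence is understated

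*Combined protocol and SAP*

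**What the plan says.** In section 5.1, under the evaluation of the practice facilitation intervention, the plan has Effectiveness "defined as the prevalence of unhealthy alcohol use at 12-months post-intervention (Jan 1, 2023-Dec. 31, 2023) as measured by AUDIT-C scores pulled from the EHR". It becomes a rate through a "denominator defined as all Veterans with a visit to PC during the practice facilitation intervention (same as for Reach outcomes". For the other half of the rate, "The numerator will be the number of Veterans with an encounter in PC who screened positive for unhealthy alcohol use", with an AUDIT-C cut-off of 5 or more, at 12 months after the intervention.

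The cohort window comes from the Adoption paragraph of the same section: "during the course of the practice facilitation intervention (July 2022-December 2022". Section 5.4 has a single criterion and no follow-up condition: "We will include all Veterans with a visit to the Pittsburgh VA primary care during the practice facilitation intervention".

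Section 5.7 describes the effectiveness analysis differently. "Effectiveness will be assessed via a time-series analysis, where the intervention site will serve as its own control", and the AUDIT-C score itself "will be modeled using a regression model with an indicator for practice facilitation (pre- vs. post-), a continuous term for time" and their interaction.

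No section says how to handle a cohort member who has no AUDIT-C recorded in 2023.

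**The concern.** The denominator is fixed by a visit in the second half of 2022. The numerator needs a positive screen at 12 months. A Veteran who died, moved away, did not return, or returned but was not screened meets the first condition and cannot meet the second. In the arithmetic of the rate, that Veteran is indistinguishable from one who was screened and scored below 5.

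The result would be labelled a prevalence of unhealthy alcohol use, but it would be the product of that prevalence and screening completeness. Section 5.1 says the measure is to serve as pilot data for a larger trial. A reader who takes the figure as a prevalence would carry too low a value into that planning and could not tell how much of it reflects missed screening.

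**Working it through.** The documents state no baseline prevalence, re-screening rate or loss to follow-up, so there is no figure of the plan's own to reproduce. The check follows from the definition. All numerical inputs below are assumptions.

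**Inputs**
- p: the share of the cohort that would score 5 or more if everyone were screened in 2023. Assumed 12%.
- s_pos and s_neg: the shares of true positives and true negatives with a 2023 AUDIT-C. Assumed 60 to 90%.
- The numerator is restricted to the cohort. This is inferred from sections 5.4 and 5.7, not stated in section 5.1.

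**Step 1. The rate as written.** Reported rate = p × s_pos. With re-screening unrelated to drinking (s_pos = s_neg = s):

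| s | Reported rate | Relative understatement |
|---|---|---|
| 90% | 0.12 × 0.9 = 10.8% | 10% |
| 80% | 0.12 × 0.8 = 9.6% | 20% |
| 70% | 0.12 × 0.7 = 8.4% | 30% |
| 60% | 0.12 × 0.6 = 7.2% | 40% |

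The relative understatement is 1 − s_pos, whatever value is assumed for p.

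**Step 2. A screened-only denominator.** Rate = p × s_pos / [p × s_pos + (1 − p) × s_neg]. When s_pos = s_neg, this returns 12% in every row above.

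**Step 3. Positives re-screened less often.** Take s_pos = 60% and s_neg = 80%.
- As written: 0.12 × 0.6 = 7.2%.
- Screened-only: 0.072 / (0.072 + 0.88 × 0.8) = 0.072 / 0.776 = 9.3%.
- True value: 12%.

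The screened-only denominator removes part of the error but not all of it.

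**Step 4. Bounds.** The rate as written is the lower bound, because every unscreened Veteran is taken as negative. The upper bound takes them all as positive: p × s + (1 − s). For s = 90, 80, 70 and 60% it is 10.8 + 10 = 20.8%, 9.6 + 20 = 29.6%, 8.4 + 30 = 38.4% and 7.2 + 40 = 47.2%.

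**Step 5. If an earlier rate were set beside it.** Suppose drinking does not change and an earlier rate is built the same way, with share s0 of positives screened then and s1 in 2023. The apparent relative change is s1/s0 − 1.
- s0 = 100%, s1 = 80%: −20%, an apparent benefit.
- s0 = 80%, s1 = 80%: 0%.
- s0 = 50%, s1 = 80%: +60%, an apparent harm.

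The sign depends on how completely the earlier period was screened, which the documents do not say.

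**The case against.** The strongest reply is that this rate does not carry the effectiveness inference. Section 5.1 gives it no pre-intervention value, comparator or test. The pre/post inference is the section 5.7 regression on AUDIT-C scores. There, a Veteran with no 2023 screen contributes no post-intervention score and is not set to negative. Missing screens are a selection question in that model, which is a different mechanism. This stands, and it limits the consequence. A reader might infer that loss to follow-up will look like a benefit, or will inflate the effect size used to plan the next trial. The documents do not support either claim: no comparison is defined for this rate, and step 5 shows that the sign could go either way. But the regression does not correct the section 5.1 rate, which remains the stated definition of Effectiveness.

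Second, the numerator is not explicitly tied to the cohort. If Veterans first seen in 2023 could enter it, they might offset the loss. Treating the 10,000 Veterans of the section 5.2 data pull as the cohort (an assumption), 80% re-screening leaves 2,000 unscreened and loses 0.12 × 2,000 = 240 positives. Another 2,000 newly seen and screened patients at the same prevalence would add 240 back. The point is fair as to wording. However, section 5.4 admits only Veterans seen during the intervention, and section 5.7 asks about those same Veterans, so a nested numerator is the natural reading. If it is not intended, numerator and denominator describe different populations, and that also needs correcting. Nor does section 5.1 say whether the encounter it mentions in the numerator must fall in 2023. The point does not depend on that, because the positive 12-month screen is enough to produce it.

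Third, this is a pilot in which the protocol itself thinks a measurable clinical effect unlikely. That lowers the stakes but does not make the rate a prevalence.

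**Conclusion.** The definition is wrong as written. Veterans without a 2023 AUDIT-C are counted as not screening positive, and with a nested numerator the 12-month prevalence is understated by the share of positives not re-screened. On the assumed inputs the understatement is 10 to 40% in relative terms, or 10.8 down to 7.2% against a true 12%. The mechanism follows from the text. The size rests on re-screening shares that the documents do not give.

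Two further readings go too far. The unscreened are not counted as abstinent, because the category is an AUDIT-C below 5. Nor is the shortfall exactly the overall fraction not re-screened, unless re-screening is unrelated to drinking.

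**What to change.** In section 5.1:
- State that the numerator is restricted to the cohort in the denominator.
- Define 12-month prevalence as cohort Veterans with AUDIT-C of 5 or more, divided by cohort Veterans with an AUDIT-C recorded in 2023. Use one pre-specified score per Veteran.
- Report the percentage of the cohort with a 2023 AUDIT-C, and deaths if vital status is available. Section 5.2 lists the Vital Status File only as a source of date of birth, so its use for deaths would have to be added.
- If any pre-intervention rate is shown, build it by the same rule and report its screening share.

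In section 5.7, add a sensitivity analysis for the unscreened. Either weight by the inverse probability of having a 2023 AUDIT-C, using the demographic, diagnosis, comorbidity and utilization variables listed in section 5.2, or give bounds as in step 4. Step 3 shows why the screened-only rate should not stand alone.

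Keep the time-series model for the pre/post inference. A simple paired before/after test would ignore the historical trend that section 5.7 chose this model to handle.

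The cost is a change of wording, a smaller denominator and one extra sensitivity analysis. Apart from vital status, the data are already listed in section 5.2, and the abstract describes extraction, cleaning and analysis as still to be completed, so the change can be made before the rate is computed.
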